### **Mindfulness Intervention**

In the EMA + Mindfulness condition, participants have a 67% chance of receiving a mindfulness exercise, unless their sad or anxious mood rating is 90 or above, in which case their chance is 85%. This graded strategy was chosen so that participants would not be able to easily figure out the mood rating that results in an exercise and so that participants would have a greater chance of receiving an exercise when they most needed it.

If an exercise is assigned, participants are prompted to enter how much time they have to engage in an activity (from 0-15 minutes). There are three 1-minute exercises (written instructions for focusing on the breath, sounds, or physical sensations); six 3-5 minute exercises (guided audio focusing on breathing, sounds, or body scan); and five 10-12 minute exercises (guided audio focusing on breath, body scan, or mountain metaphor).

Participants who indicate having less than 5 minutes receive one of the 1-minute exercises, those who indicate having at least 5 minutes receive either a 1-minute or a 3-5 minute exercise, and those who indicate having at least 12 minutes receive any exercise. Exercises are randomly assigned based on these parameters. The guided audio exercises were chosen based on those freely available that represent the type of mindfulness exercises typically found in MBSR courses, appeared accessible for adolescents, featured a variety of voices, and performed well in pilot testing. Following each mindfulness exercise, participants were prompted with the same EMA questions plus an additional question asking how helpful the activity was, rated on a 0-100 sliding scale.

### **Data Handling and Record Keeping**

All data (EMA, questionnaire) will be stored electronically and password protected using only an ID number (i.e., without identifying information). The PI will maintain a password protected document linking ID numbers to participant names. A paper copy of information that includes identifying information will be stored in a locked file cabinet in a locked room in a folder labeled with an ID number.

The PI will put several actions in place to assure quality of data collected in the study. The PI will oversee recruitment and enrollment and assure that enrollment targets are met. The PI will be in close contact with the research associate who managed recruitment and enrollment and updates will be monitored weekly. The PI will also oversee data collection and management to insure its validity and integrity. Only key project personnel will have access to the data. Any personnel doing data analysis will work with a copy of the data to avoid any changes being made to original data files. The PI will assure that the dissemination plan is followed. Finally, all project staff, including the PI will complete a Good Clinical Practice training course (e.g., <https://gcp.nidatraining.org/>).

### **Assessment of Safety**

Questionnaires assessing self-injury (including suicidal thoughts and behaviors) will be collected from adolescents at four time points (baseline, post-intervention, and three follow-up periods). Participants who indicate suicidal ideation (by responding to an item on the Children's Depression Inventory indicating that they want to kill themselves, i.e., scoring a 3 on item 9) or serious self-injurious behavior (by responding affirmatively to questions on the Self-injurious Thoughts and Behaviors inventory indicating having a suicide plan or attempt in the past year/week/since the last assessment) will be contacted by the PI, a licensed clinical psychologist with extensive experience doing research and treatment for self-injury. The PI will assess risk by talking with the participant and determine whether contact with a mental health professional is warranted. If necessary, the PI will talk with the adolescent's parent to determine whether the participant is currently in treatment, and if so, will advise the parent and adolescent to make contact with their mental health professional. If a participant requests confidentiality regarding serious self-injurious behavior, we will remind them that this is one of the exceptions to confidentiality because we are seriously concerned for their safety. Every effort will be made to allow the adolescent some control in how the information is presented to the parent (i.e., the adolescent tells the parent or the PI tells the parent), but serious concerns will be communicated with parents, regardless, for safety. For participants not currently under the care of a mental health professional, we will provide a list of local mental health resources and help the family with the referral. We will re-contact families to monitor the participants and determine whether contact with a mental health professional has been made. For participants deemed in imminent risk of suicide, we will inform the parent and advise them to transport the subject to an emergency room or call 911 for assistance with transportation.

Participants will report on their daily mood during the active intervention period (three weeks) and during the optional follow up periods (6 months). In order to monitor and address any potential distress or dissatisfaction during the active intervention period, we will invite participants to contact us with concerns. During our twice-weekly emails to motivate

participants, we will tell them that they should contact us if they are having any difficulties or feeling upset so that we can talk with them by phone and intervene as needed (e.g., conduct a suicide safety assessment as described above).

In all cases, we will document conversations and interactions with subjects and any health professionals they ask us to contact on their behalf. We will also report any adverse events or unanticipated problems to the appropriate party (e.g., IRB). Because of the low risk involved in the proposed study, the PI will be responsible for carrying out this data and safety monitoring plan.

### **Adverse Event**

We do not anticipate any risks, as no serious adverse events have been reported in the literature with respect to brief mindfulness interventions. Potential serious adverse events would include hospitalization and suicide attempt. To protect participants against foreseeable risks, participants who indicate serious suicidal concerns will be excluded from or withdrawn from the study until these concerns are resolved. Potential adverse events may include increases in suicidal thoughts or behaviors, breach of confidentiality, upsetting experiences, distress or dissatisfaction as the result of assessment or use of the app. We will ask both participants and their parents about any adverse events that may have occurred during the active intervention period (e.g., upsetting experiences, distress or dissatisfaction as the result of assessment or use of the app). Adverse and serious adverse events will be reported to the appropriate individuals (see section below).

Written informed consent and assent will be obtained by trained research assistants (RAs) during the laboratory visit to Lawrence University at the beginning of the study. The RA will bring the parent and adolescent into a private room and read the assent form to the adolescent. The RA will ask the parent and adolescent separately if they have any questions about the study and answer them. If the parent signs the written consent form, then the RA will say to the adolescent, "Would you like to be in the study and complete the activities? If you say yes, this means you have read this paper or had it read to you and want to be in the study. If you say no, that means you do not want to be in the study. You can say yes or no. Being in the study is your choice. No one will be mad or upset if you do not say yes, sign this paper, or even change your mind later." If the adolescent indicates a definite "yes", the RA will obtain their signature and certify the assent procedure was followed.

To protect against a potential breach of confidentiality, the EMA data are stored on a secure, password protected website, without any identifying information. The questionnaire data are also stored on a secure, password protected website, without any identifying information. Data collected during the first lab visit are obtained in separate, private rooms for each parent and child. Family background and contact information (i.e., identifying information) will be collected on paper and stored in a locked file cabinet in a locked room only accessible to study staff. No information collected from the adolescent participants will be shared with parents unless there are serious concerns about the child's safety (i.e., suicide concerns or child abuse). Participants and project staff will communicate via phone, email, and text regarding scheduling and completing study materials, but no data or sensitive information will be shared.

The trial will be stopped should findings suggest that the intervention is resulting in mean suicide and/or self-injury levels to increase to a level of clinical concern (e.g., ideation with a plan, attempts, or completions).

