### **Procedure**

Participants and a parent or guardian will come to the laboratory to provide written assent and consent, complete baseline questionnaires, and get the mobile application and instructions. The lab visit will last approximately 40 minutes. We will put the application on participants' own mobile devices (Android or iOS platform) if they have them and loan mobile devices (Android phones without calling services) to participants who do not have their own. The active intervention period will last three weeks, during which time participants will be

asked to use the application at least three times per day. Undergraduate research assistants (RAs) masked to condition will monitor daily use via the database where responses are logged. Midway through each week of the active intervention period, RAs will send reminder messages for motivation and encouragement. A small bonus (\$5 per week) will be offered to participants for protocol compliance (i.e., using the app 21 times that week). The weekly emails will let participants know whether they were on track to receive the bonus or encourage them to use the app more regularly. At the end of three weeks (i.e., post), participants will be notified to complete questionnaires online. At this time, participants still have the opportunity to use the mobile application, but they will not be reminded to use it so that we can monitor self-motivated use. All use will be monitored electronically through a database that tracks responses with time stamps. After six weeks, participants will again be notified to complete questionnaires online (follow-up 1). Finally, after an additional six weeks (approximately 3 months after post), participants will be notified to complete questionnaires online (follow-up 2) and return borrowed phones if applicable (via drop-off, pick up or mail). The total time that participants' use is monitored will be 15 weeks (i.e., 3 weeks for the active intervention period and 12 weeks of follow up). See Figure 1 for depiction of timeline.

[figure not shown]

Figure 1. Overview of participant activities and compensation.

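### The SAP imputes missing questionnaires only if they are missing completely at random; this is the wrong condition, and the protocol's own suicidality withdrawal rule gives a case where it fails

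*Combined protocol and SAP*

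**What the plan says.** **Missing data.** The Statistical Analysis Plan (General Analytic Strategies) gives one rule for missing questionnaires: multiple imputation, on condition that the data are missing completely at random (MCAR). It does not say what happens otherwise. It also compares completers with dropouts, but only to describe external validity. The maximum likelihood estimation under Specific Aim 2 belongs to the multilevel models of the momentary (EMA) data, not to the questionnaires.

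**Withdrawal.** The Adverse Event section says that "participants who indicate serious suicidal concerns will be excluded from or withdrawn from the study until these concerns are resolved".

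**Detection.** Assessment of Safety has the principal investigator (PI) contact anyone "scoring a 3 on item 9" of the Children's Depression Inventory (CDI), or answering the self-injury questionnaire (SITBI) in a way "indicating having a suicide plan or attempt in the past year/week/since the last assessment". Risk assessment and referral follow, and then: "We will re-contact families to monitor the participants and determine whether contact with a mental health professional has been made".

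**Analysis.** Specific Aim 2 analyses depression, anxiety, parent-reported internalizing symptoms and self-injury at post and at both follow-ups. The later waves are used to judge whether effects last or appear late. On timing, Procedure says: "After six weeks, participants will again be notified to complete questionnaires online (follow-up 1"). Follow-up 2 comes six weeks after that.

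**The concern.** The MCAR condition works backwards. Under MCAR, complete cases already give unbiased estimates and imputation mainly adds precision. When missingness depends on data already recorded (missing at random, MAR), complete cases can be biased and imputation from those data can correct them. That is where the SAP's wording rules imputation out and leaves the analyst without a prespecified method.

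The withdrawal rule makes this concrete. The text withdraws participants from the study, not merely from the app, and nothing says that their questionnaires continue. A wave missed for this reason is missing because of suicidality, which is part of the self-injury outcome and of the CDI score. It cannot be MCAR. If one arm has more such withdrawals, that arm loses more of its worst scores and the follow-up difference shrinks. The post comparison is largely unaffected, because a concern reported at post is already on file.

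**Working it through.** The plan states no trigger, withdrawal or resolution rate, and no SD, so it has no figure to reproduce. The size below is an illustration on assumed inputs.

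**From the documents.** 150 participants at 1:1, so about 75 per arm (Sample). Six weeks between post and follow-up 1, and again to follow-up 2 (Procedure).

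**Assumed.**
- Scores are standard normal at the trigger wave and at the next wave, with correlation r = 0.7.
- The true benefit is d = 0.2 to 0.3 SD at both waves.
- The control trigger rate is pc = 1% to 10%. The low end allows for the same rule also excluding such adolescents at entry.
- f is the share of triggered participants who are withdrawn and still out at the next wave, 0.25 to 0.5. For example, half withdrawn and half of those unresolved gives 0.25.
- Observed cases are analysed. The SAP does not say this; it is the natural default when imputation is ruled out.

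**Formulas.** The cut-off is c = z(1 − pc) for control and z(1 − pc) + d for intervention, measured from each arm's own mean. Then p = 1 − Φ(c) and L = φ(c)/p. The amount by which an arm's observed mean is lowered at the next wave is r × L × pf/(1 − pf). The hidden part of the difference is the control loss minus the intervention loss.

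**Worked case, pc = 0.10, d = 0.3, f = 0.5.**
- Control: L = 1.755, pf = 0.05; 0.7 × 1.755 × 0.05/0.95 = 0.0647.
- Intervention: p = 0.0569, L = 2.008, pf = 0.0285; 0.7 × 2.008 × 0.0285/0.9715 = 0.0411.
- Hidden: 0.0235 SD (from unrounded terms).

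**Range.** The unadjusted standard error is √(2/75) = 0.163 SD.

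| Control trigger rate | f | Hidden, d = 0.2 to 0.3 (SD) | In standard errors | Controls out, of 75 |
|---|---|---|---|---|
| 1% to 2% | 0.25 | 0.002 to 0.004 | 0.01 to 0.03 | 0.2 to 0.4 |
| 1% to 2% | 0.5 | 0.004 to 0.008 | 0.02 to 0.05 | 0.4 to 0.8 |
| 5% to 10% | 0.25 | 0.005 to 0.011 | 0.03 to 0.07 | 0.9 to 1.9 |
| 5% to 10% | 0.5 | 0.011 to 0.024 | 0.07 to 0.14 | 1.9 to 3.8 |

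With d = 0 the two losses are equal and nothing is hidden.

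**Does imputation help?** In a simulation of this model with 4 million per arm, the next wave was imputed within arm from the trigger-wave score. The remaining bias is 0.000 SD when resolution is unrelated to later severity. If those still out are the worst off (trigger rates 5% to 10%, f = 0.25 to 0.5), the bias is 0.010 to 0.037 SD without imputation and 0.004 to 0.017 SD with it.

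**The case against.** **The link is inferred.** The withdrawal sentence does not define serious suicidal concerns and does not refer to the CDI and SITBI triggers. Assessment of Safety, the operational procedure, has no withdrawal step and does not say that questionnaires stop. This stands as a limit. Those withdrawn may be only some of those triggered, and the sponsor may intend only a pause of the app. It does not rescue the MCAR condition, which is wrong for any outcome-related dropout.

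**The effect is small, and the model is not the planned analysis.** This also stands. Specific Aim 2 tests indirect effects through rumination, whereas the working uses a mean difference on one normal variable that serves as both trigger and outcome. The real triggers are a few items, self-injury scores are likely to be skewed, and the anxiety and parent-reported scores would presumably be less affected. Ordinary dropout may well matter more.

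**Stronger readings that a reader might infer.**
- That the follow-up self-injury contrast would vanish. An example can be built: 10% versus 5% with concerns at post, half of them unresolved and all of those missing, and 2% new cases. The true follow-up rates are then 6.8% versus 4.4%, while complete cases show 1.9% in both arms. Every rate here is assumed, as is the loss of every unresolved case. The documents support neither.
- That the stopping rule is blinded. The rule looks for findings "resulting in mean suicide and/or self-injury levels to increase to a level of clinical concern", and its examples include plans and attempts. Those answers are recorded before any withdrawal. Adverse-event reporting continues as well: "Potential serious adverse events would include hospitalization and suicide attempt". In the model with trigger rates of 5% to 10%, a harm of 0.2 to 0.3 SD would be understated at the later wave by 0.007 to 0.029 SD for f = 0.25 to 0.5. One signal is slightly weakened and none is removed.

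**Conclusion.** The firm defect is the MCAR condition with no alternative. It needs no assumption beyond the SAP's own text. The suicidality withdrawal is a case where the condition must fail, provided that withdrawal from the study includes its questionnaires, which is the plain but not the explicit reading.

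The likely size of this one route is about 0.002 to 0.024 SD in a simple follow-up mean difference (0.01 to 0.14 of a standard error), for assumed trigger rates of 1% to 10% and f of 0.25 to 0.5. It is zero if withdrawal and severity are equal by arm. No bias in the indirect effect has been shown, and the effect on the stopping rule is minor. The change is worth making because the stated rule is wrong and a better one costs almost nothing, not because a large bias is expected. Confidence is medium.

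**What to change.** **Main change, SAP (General Analytic Strategies).**
1. Delete the MCAR condition. Analyse all participants as randomised, with multiple imputation under MAR using arm and all earlier questionnaire scores, including CDI and SITBI.
2. Add a sensitivity analysis that shifts imputed values upward for participants withdrawn for safety. The residual 0.004 to 0.017 SD in the working is the reason.
3. Report safety withdrawals by arm.

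This costs SAP wording and some analysis time. It uses data already collected.

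**Secondary change, protocol (Adverse Event).** State that a safety withdrawal after randomisation pauses app use, while the scheduled online questionnaires continue for those who agree and for whom the PI judges it safe. This needs protocol wording and IRB agreement. Its real cost is some assessment burden for at-risk adolescents: the protocol itself lists "distress or dissatisfaction as the result of assessment or use of the app" among potential adverse events. Participants' agreement and the PI's judgement limit that burden. If the sponsor already intends questionnaires to continue, one sentence saying so is enough.

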### **Statistical Analysis Plan**

**General Analytic Strategies.** The number of participants recruited and retained will be documented, and comparisons will be made on all study variables between those who complete and those who drop out of the study in order to inform external validity. Compliance and intervention dose will be assessed with time-stamped electronic records generated through the app. All data will be inspected for normality and transformations will

be applied as needed. Missing questionnaire data will be handled using multiple imputation if data are missing completely at random (Enders, 2013).

**Specific Aim 1.** There are multiple ways to assess participants' engagement to determine the acceptability of the intervention. The first two involve examining how much adolescents use the mobile application. We will examine compliance during the 3-week intervention period by comparing the amount of application use (as recorded electronically) in the intervention group to the control group. We will also examine use during the follow-up periods (12 weeks), when it is optional. Both of these usage questions can be answered with t-tests comparing use between groups.

The other two ways of measuring acceptability are more direct. Participants will complete a satisfaction questionnaire during the post-assessment, and we will compare scores on these questions between groups using t-tests. Finally, participants in the intervention condition will answer a question after each mindfulness exercise regarding how helpful it was using a 0-100 scale ranging from not at all helpful to extremely helpful. Scores on this question can be averaged and examined separately for each type of mindfulness exercise to see if they fall above the benchmark of 50, indicating that adolescents find them helpful in the moment. With all statistical analyses, we will use best current practices regarding correction for multiple tests.

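### The general adverse-event question covers only the 3-week active period; in the 12-week follow-up, hospitalization, app-related distress and parent-reported adverse events have no planned query

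*Combined protocol and SAP*

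**What the plan says.** The Adverse Event section contains the only general adverse-event question in the plan. It is put to both adolescents and parents and concerns "adverse events that may have occurred during the active intervention period". Its examples are upset, distress or dissatisfaction arising from the assessments or the app. The same section defines the serious category: "Potential serious adverse events would include hospitalization and suicide attempt". It also lists increases in suicidal thoughts or behaviors among the possible adverse events.

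The Procedure section fixes the window: "The active intervention period will last three weeks". After that, "participants still have the opportunity to use the mobile application, but they will not be reminded to use it". Total monitoring of use "will be 15 weeks (i.e., 3 weeks for the active intervention period and 12 weeks of follow up". The SAP treats the later weeks as a period of interest under Specific Aim 1: "We will also examine use during the follow-up periods (12 weeks), when it is optional". Under Specific Aim 2 it tests the indirect-effect models at post, follow-up 1 and follow-up 2.

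The Assessment of Safety section adds three things. Self-injury questionnaires are collected through follow-up, and the suicide plan and attempt items can refer to the time since the last assessment. Certain answers lead to contact by the principal investigator. Participants are invited to get in touch if distressed, but that invitation is tied to the active period. The section also commits to report any adverse events, with no time limit.

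**The concern.** The window of the general question is much shorter than the period over which the app is available and outcomes are analysed. The plan treats voluntary use in weeks 4 to 15 as evidence of engagement and looks for maintained or delayed effects in those weeks. Harms other than self-injury and suicidality are not sought over the same time.

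Three kinds of event are affected: a hospitalization, distress caused by the app or by answering the questions, and anything a parent has noticed that the adolescent does not report. If such events come to light only when a family happens to mention them, the count is incomplete. It may also be incomplete to different degrees in the two arms, because only the EMA + Mindfulness version delivers exercises and continued use may differ by arm. A low count in weeks 4 to 15 could then mean few events or few reports, and the data could not tell these apart.

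**Working it through.** **1. Reproduce the monitored period.** From the Procedure section: active period 3 weeks; follow-up 1 six weeks after post; follow-up 2 a further six weeks on.

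- Follow-up = 6 + 6 = 12 weeks.
- Total = 3 + 12 = 15 weeks, which matches the stated total.

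**2. Share of calendar time covered by the general question.**

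- Inside the window: 3 / 15 = 0.20.
- Outside the window: 12 / 15 = 0.80.

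**3. Sensitivity to the conflict over follow-up length.** The Assessment of Safety section gives the optional follow-up as 6 months, against 12 weeks in the Procedure section and the SAP. Taking 6 months as 24 to 26 weeks (an assumption):

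- 24 / (3 + 24) = 24 / 27 = 0.89.
- 26 / (3 + 26) = 26 / 29 = 0.90.

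The share outside the window is therefore 80% on the Procedure and SAP figures, and 89% to 90% on the other.

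**4. What is asked, by type of event.** This uses the instruments as described under Questionnaires, Assessment of Safety and Adverse Event.

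| Event | Weeks 1–3 | Weeks 4–15 |
|---|---|---|
| Suicidal thoughts, plan, attempt; self-injury | Asked at post (CDI, SITBI) and by the general question | Asked at both follow-ups (CDI, SITBI) |
| Hospitalization | General question | No item described |
| Distress from app or assessment | General question; invitation to make contact; satisfaction form at post | No item described |
| Adverse events reported by a parent | General question | No item described; the parent completes the 5-item internalizing subscale |

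The first row has a planned query throughout. The other three lose theirs after week 3.

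**5. Could another step fill the gap?**

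- The invitation to report distress is carried by the motivational emails. The Procedure section places its reminder messages in the active period and stops reminders afterwards.
- Mood ratings in the app exist only when the app is opened, and no safety review of them is described. An adolescent who stops using the app because it is upsetting supplies none.
- The commitment to report adverse events says what happens once an event is known. It does not say how an event in weeks 4 to 15 becomes known.
- The SAP contains no summary of adverse events by arm.

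**6. Coverage after the change.** With the question at post, follow-up 1 and follow-up 2, each referring to the time since the last assessment, the windows are 3 + 6 + 6 = 15 weeks, or 15 / 15.

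**The case against.** The strongest reply is that the most important harms are already followed to the end. The protocol itself classes increased suicidal thoughts or behaviors as adverse events and a suicide attempt as a serious one. Both are asked about at follow-up 1 and follow-up 2, with a recall window that can span the interval and with contact by the principal investigator when answers are worrying. The rule for stopping the trial rests on suicide and self-injury levels, which are measured through follow-up 2. All of this stands. A reader might infer that adverse events go unasked after week 3, or that four fifths of exposure has no safety query. The documents do not support either reading.

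The 80% also needs care. It is a share of calendar time in which the app is available, not of exposure. Use after week 3 is voluntary and unprompted, its amount is unknown in advance, and the EMA-only arm receives no exercises at any time.

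A reader might further infer that the trial's whole safety conclusion would rest on three weeks of data. The plan states no such conclusion, and its self-injury data run to follow-up 2. At most the remark applies to events other than self-injury and suicidality.

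Some other events could also come to light indirectly. A hospitalization linked to a suicide attempt would probably emerge when the principal investigator contacts the adolescent or the family.

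Finally, in a study described as low risk, concentrating a question about app-related distress on the weeks of prompted use is a defensible choice. That limits the weight of the point but does not answer it: hospitalization is a serious event by the protocol's own definition, and the expectation of low risk is something the question would help to check.

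**Conclusion.** The point holds in a limited form. The general adverse-event question to adolescents and parents covers 3 of 15 monitored weeks. In the other 12 weeks (80% of calendar time), self-injury and suicidality are still asked about systematically. Hospitalization, distress from the app or assessments, and parent-reported adverse events have no planned query. Such events would be found mainly if volunteered, or if they surfaced through a contact about suicidality.

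This rests on two assumptions. The first is that the follow-up instruments ask only what the plan describes; their item lists are not in the documents. The second is that follow-up lasts 12 weeks. The 6-month figure in the Assessment of Safety section must be reconciled with that, as must the same section's count of four assessment times against the five it lists (baseline, post and three follow-ups). Neither conflict removes the gap; the longer follow-up would widen it. The gap does not threaten the trial's main analyses, but it is real, comes from a stated rule, and is inexpensive to close.

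**What to change.** Change the sentence in the Adverse Event section so that the question covers the whole monitored period. Add the same question, with hospitalization named, to the adolescent and parent online questionnaires already scheduled at follow-up 1 and follow-up 2, each referring to the time since the last assessment. Add a line to the SAP stating that adverse and serious adverse events will be reported as counts by arm. Separating the active period from follow-up would keep prompted and optional use distinct. In the same edit, reconcile the follow-up length and the number of assessment times across the Procedure, Questionnaires, Assessment of Safety and SAP sections.

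The cost is one or two items on each form and a small added load in recording and reporting events. No visit is added.
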